Appendix B

PedsQLTM
Pediatric Quality of Life
Inventory
Version 4.0
PARENT REPORT for CHILDREN (ages 8-12)

DIRECTIONS

On the following page is a list of things that might be a problem for **your child**.

Please tell us **how much of a problem** each one has been for **your child**

during the **past ONE month** by circling:

0 if it is **never a problem**

1 if it is **almost never a problem**

2 if it is **sometimes a problem**

3 if it is **often a problem**

4 if it is **almost always a problem**

There are no right or wrong answers.

If you do not understand a question, please ask for help.

*In the past **ONE month**, how much of a **problem** has your child had with*

PHYSICAL FUNCTIONING (problems with...)	Never	Almost Never	Sometimes	Often	Almost Always
1. Walking more than one block	0	1	2	3	4
2. Running	0	1	2	3	4
3. Participating in sports activity or exercise	0	1	2	3	4
4. Lifting something heavy	0	1	2	3	4
5. Taking a bath or shower by him or herself	0	1	2	3	4
6. Doing chores around the house	0	1	2	3	4
7. Having hurts or aches	0	1	2	3	4
8. Low energy level	0	1	2	3	4

EMOTIONAL FUNCTIONING (problems with...)	Never	Almost Never	Sometimes	Often	Almost Always
1. Feeling afraid or scared	0	1	2	3	4
2. Feeling sad or blue	0	1	2	3	4
3. Feeling angry	0	1	2	3	4
4. Trouble sleeping	0	1	2	3	4
5. Worrying about what will happen to him or her	0	1	2	3	4
SOCIAL FUNCTIONING (problems with...)	Never	Almost Never	Sometimes	Often	Almost Always
1. Getting along with other children	0	1	2	3	4
2. Other kids not wanting to be his or her friend	0	1	2	3	4
3. Getting teased by other children	0	1	2	3	4
4. Not able to do things that other children his or her	0	1	2	3	4
5. Keeping up when playing with other children	0	1	2	3	4
SCHOOL FUNCTIONING (problems with...)	Never	Almost Never	Sometimes	Often	Almost Always
1. Paying attention in class	0	1	2	3	4
2. Forgetting things	0	1	2	3	4
3. Keeping up with schoolwork	0	1	2	3	4

4. Missing school because of not feeling well	0	1	2	3	4
5. Missing school to go to the doctor or hospital	0	1	2	3	4

Appendix C

TM
PedsQL
 Pediatric Quality of Life
 Inventory

Version 4.0
CHILD REPORT (ages 8-12)

DIRECTIONS

On the following page is a list of things that might be a problem for you.

Please tell us **how much of a problem** each one has been for you
 during the **past ONE month** by circling:

- 0** if it is **never** a problem
- 1** if it is **almost never** a problem
- 2** if it is **sometimes** a problem
- 3** if it is **often** a problem
- 4** if it is **almost always** a problem

There are no right or wrong answers.
 If you do not understand a question, please ask for help.

*In the past **ONE month**, how much of a **problem** has this been for you ...*

ABOUT MY HEALTH AND ACTIVITIES (problems with...)	Never	Almost Never	Sometimes	Often	Almost Always
1. It is hard for me to walk more than one block	0	1	2	3	4
2. It is hard for me to run	0	1	2	3	4
3. It is hard for me to do sports activity or exercise	0	1	2	3	4
4. It is hard for me to lift something heavy	0	1	2	3	4
5. It is hard for me to take a bath or shower by myself	0	1	2	3	4
6. It is hard for me to do chores around the house	0	1	2	3	4
7. I hurt or ache	0	1	2	3	4
8. I have low energy	0	1	2	3	4

ABOUT MY FEELINGS (problems with...)	Never	Almost Never	Sometimes	Often	Almost Always
1. I feel afraid or scared	0	1	2	3	4
2. I feel sad or blue	0	1	2	3	4
3. I feel angry	0	1	2	3	4
4. I have trouble sleeping	0	1	2	3	4
5. I worry about what will happen to me	0	1	2	3	4

How I GET ALONG WITH OTHERS (problems with...)	Never	Almost Never	Sometimes	Often	Almost Always
1. I have trouble getting along with other kids	0	1	2	3	4
2. Other kids do not want to be my friend	0	1	2	3	4
3. Other kids tease me	0	1	2	3	4
4. I cannot do things that other kids my age can do	0	1	2	3	4
5. It is hard to keep up when I play with other kids	0	1	2	3	4
ABOUT SCHOOL (problems with...)	Never	Almost Never	Sometimes	Often	Almost Always
1. It is hard to pay attention in class	0	1	2	3	4
2. I forget things	0	1	2	3	4
3. I have trouble keeping up with my schoolwork	0	1	2	3	4
4. I miss school because of not feeling well	0	1	2	3	4
5. I miss school to go to the doctor or hospital	0	1	2	3	4

Appendix D

PedsQLTM
Pediatric Quality of Life
Inventory

Version 4.0
PARENT REPORT for TEENS (ages 13-18)

DIRECTIONS

On the following page is a list of things that might be a problem for **your teen**.

Please tell us **how much of a problem** each one has been for **your teen**
during the **past ONE month** by circling:

- 0** if it is **never** a problem
- 1** if it is **almost never** a problem
- 2** if it is **sometimes** a problem
- 3** if it is **often** a problem
- 4** if it is **almost always** a problem

There are no right or wrong answers.
If you do not understand a question, please ask for help.

*In the past **ONE month**, how much of a **problem** has your teen had with ...*

PHYSICAL FUNCTIONING (PROBLEMS WITH...)	Never	Almost Never	Sometimes	Often	Almost Always
1. Walking more than one block	0	1	2	3	4
2. Running	0	1	2	3	4
3. Participating in sports activity or exercise	0	1	2	3	4
4. Lifting something heavy	0	1	2	3	4
5. Taking a bath or shower by him or herself	0	1	2	3	4
6. Doing chores around the house	0	1	2	3	4
7. Having hurts or aches	0	1	2	3	4
8. Low energy level	0	1	2	3	4

EMOTIONAL FUNCTIONING (PROBLEMS WITH...)	Never	Almost Never	Sometimes	Often	Almost Always
1. Feeling afraid or scared	0	1	2	3	4
2. Feeling sad or blue	0	1	2	3	4
3. Feeling angry	0	1	2	3	4
4. Trouble sleeping	0	1	2	3	4
5. Worrying about what will happen to him or her	0	1	2	3	4

SOCIAL FUNCTIONING (PROBLEMS WITH...)	Never	Almost Never	Sometimes	Often	Almost Always
1. Getting along with other teens	0	1	2	3	4
2. Other teens not wanting to be his or her friend	0	1	2	3	4
3. Getting teased by other teens	0	1	2	3	4
4. Not able to do things that other teens his or her age can do	0	1	2	3	4
5. Keeping up with other teens	0	1	2	3	4

SCHOOL FUNCTIONING (PROBLEMS WITH...)	Never	Almost Never	Sometimes	Often	Almost Always
1. Paying attention in class	0	1	2	3	4
2. Forgetting things	0	1	2	3	4
3. Keeping up with schoolwork	0	1	2	3	4
4. Missing school because of not feeling well	0	1	2	3	4
5. Missing school to go to the doctor or hospital	0	1	2	3	4

PedsQLTM
Pediatric Quality of Life
Inventory

Version 4.0
TEEN REPORT (ages 13-18)

DIRECTIONS

On the following page is a list of things that might be a problem for you.

Please tell us **how much of a problem** each one has been for you
during the **past ONE month** by circling:

- 0** if it is **never** a problem
- 1** if it is **almost never** a problem
- 2** if it is **sometimes** a problem
- 3** if it is **often** a problem
- 4** if it is **almost always** a problem

There are no right or wrong answers.
If you do not understand a question, please ask for help.

*In the past **ONE month**, how much of a **problem** has this been for you ...*

ABOUT MY HEALTH AND ACTIVITIES (problems with...)	Never	Almost Never	Sometimes	Often	Almost Always
1. It is hard for me to walk more than one block	0	1	2	3	4
2. It is hard for me to run	0	1	2	3	4
3. It is hard for me to do sports activity or exercise	0	1	2	3	4
4. It is hard for me to lift something heavy	0	1	2	3	4
5. It is hard for me to take a bath or shower by myself	0	1	2	3	4
6. It is hard for me to do chores around the house	0	1	2	3	4
7. I hurt or ache	0	1	2	3	4
8. I have low energy	0	1	2	3	4

ABOUT MY FEELINGS (problems with...)	Never	Almost Never	Sometimes	Often	Almost Always
1. I feel afraid or scared	0	1	2	3	4
2. I feel sad or blue	0	1	2	3	4
3. I feel angry	0	1	2	3	4
4. I have trouble sleeping	0	1	2	3	4
5. I worry about what will happen to me	0	1	2	3	4
How I GET ALONG WITH OTHERS (problems with...)	Never	Almost Never	Sometimes	Often	Almost Always
1. I have trouble getting along with other teens	0	1	2	3	4
2. Other teens do not want to be my friend	0	1	2	3	4
3. Other teens tease me	0	1	2	3	4
4. I cannot do things that other teens my age can do	0	1	2	3	4
5. It is hard to keep up with my peers	0	1	2	3	4
ABOUT SCHOOL (problems with...)	Never	Almost Never	Sometimes	Often	Almost Always
1. It is hard to pay attention in class	0	1	2	3	4
2. I forget things	0	1	2	3	4
3. I have trouble keeping up with my schoolwork	0	1	2	3	4
4. I miss school because of not feeling well	0	1	2	3	4
5. I miss school to go to the doctor or hospital	0	1	2	3	4

Appendix F

Case# _____

Understanding the Impact of Asthma in Academic Achievement, School Attendance, and in the Quality of Life in Middle school aged children Questionnaire Using The NAEPP, 2007 guidelines

The next series of questions will ask about your child's severity of asthma, it is important that everyone give us accurate answers. The team members will not share or discuss any personal information without your permission. Only the other team members will be able to see your answers to questions or your name. Everything is kept private and strictly confidential. None of your answers will in any way affect your medical care, benefits, any services you may be receiving (such as Medicaid or WIC) or your job or immigration status. You can decide at any point not to participate in the study, and your decision won't have any impact on your current or future medical care. If you have any questions, please let me know. If not, we can start.

The next series of questions will ask about child's asthma over the past 2-4 weeks. Please listen to all the possible responses and then pick the one that best describes the child situation. You must pick the single best answer that describes the child's situation over the prior 2-4 weeks.

So think about the last 2-4 weeks....

1...how often during the day did _____ have asthma symptoms?

5-11 years			
	Severity		Control
a	<2d/wk	a	< 2d/wk but not > 1x/d
b	>2d/wk but not daily	b	>2d/wk or many times on < 2d/wk
c	Daily		
d	Throughout the day	c	Throughout the day

> 12 years			
	Severity		Control
a	<2d/wk	a	< 2d/wk but not > 1x/d
b	>2d/wk but not daily	b	>2d/wk or many times on < 2d/wk
c	Daily		
d	Throughout the day	c	Throughout the day

2...how often during the night did _____ awake due to asthma symptoms?

5-11 years			
	Severity		Control
a	<2x/month	a	0-1x/month
b	3-4 x/month	b	>2x/month
c	>1x/wk but not nightly	c	>2x/wk
d	Often 7x/wk		

> 12 years			
	Severity		Control
a	<2x/month	a	< 2x/month
b	3-4 x/month	b	1-3x/wk
c	>1x/wk but not nightly	c	>4x/wk
d	Often 7x/wk		

3...how often during the night did _____ use albuterol, quick relief medicines, for asthma symptoms? (please do not include albuterol before exercise or heavy play to avoid wheezing due to exercise).

5-11 years			
	Severity		Control
a	<2d/wk	a	< 2d/wk
b	>2d/wk but not daily	b	>2d/wk
c	Daily		
d	several x/d	c	several x/d

≥ 12 years			
	Severity		Control
a	<2d/wk	a	< 2d/wk
b	>2d/wk but not daily	b	>2d/wk
c	Daily		
d	Several x/d	c	Throughout the day

4...how often did asthma interfere with the childs normal activity.

5-11 years			
	Severity		Control
a	None	a	none
b	minor limitation	b	some limitation

c	some limitation		
d	extremely limited	c	extremely limited

≥ 12 years			
	Severity		Control
a	None	a	none
b	minor limitation	b	some limitation
c	some limitation		
d	extremely limited	c	extremely limited

5...Now I need to know how many separate times child took steroids by mouth over the last year to treat an asthma attack. A steroid by mouth is a pill or syrup that is taken for a short period of time to treat asthma attacks.

5-11 years			
	Severity		Control
a	0-1/last year	a	0-1/last year
b	>2x last year	b	>2x last year

≥12 years			
	Severity		Control
a	0-1/last year	a	0-1/last year
b	>2x last year	b	>2x last year

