Demographic information will be obtained by a structured interview; the questionnaire (Appendix A) will be used on both cases and controls: the parent/caregiver will be asked about the child's age, gender, race/ethnicity, insurance type. health care utilization, medications usage, highest level of education of the parent/ caregiver, income of the household, and parental report of school services. Cases will complete an additional 11 questions to determine asthma severity to determine NAEPP score and the Asthma Control Test (ACT) score (Appendix F and G).

We will utilize the child's electronic medical record (Cerner for ED charts and eClinicalWorks for the IMPACT DC charts) to determine insurance type and health care utilization. We will also determine each participant's weight and height from the medical record and will access medical records for the period of time we are collecting report cards for to determine clinical information, such as number of ED visits and hospitalizations over the 14 month period that the report cards cover (August 2015-November 2016).

Reporting of Academic Achievement and School Attendance

At the time of recruitment, families will be given a self-addressed, stamped envelope to send the child's 2013 first term (if available), standardized test score report (if available), and final report card to the research team. All report cards/score reports will be returned to the family via US Mail. Academic achievement, standardized test scores, and school attendance will be recorded from the report cards. All report cards in the DCPS system use the same grading scale..

The Self-Perception Profile

The self-perception profile is a reliable validated 6 question questionnaire for children in grades 6-8 that allows a child to self-evaluate their feelings about their engagement in school and their own school performance.

Reporting of the Quality of Life using the Peds QL 4.0 Form

QOL will be measured using the validated PedsQL 4.0 for children, teens, and parents (Appendices B, C, D, and E). The PedsQL 4.0 has four scales with 23 questions which ascertain physical functioning, emotional functioning, social functioning, and school functioning. A 5-point Likert scale is used in the child self-report and for the parent proxy reports. Items are reverse scored and linearly transformed to a 0 to 100 scale (0=100, 1=75, 2=50, 3=25, and 4=0), so higher scores indicate better QOL.

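### Appendix F item 3 asks about night-time albuterol use but offers whole-day answers, so the rescue-use item in the NAEPP severity and control interview can be understated

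*Combined protocol and SAP*

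**What the plan says.** Section D (Demographic Data for Cases and Controls) states the purpose of the interview: "Cases will complete an additional 11 questions to determine asthma severity to determine NAEPP score and the Asthma Control Test (ACT) score". The NAEPP items are in Appendix F and the Asthma Control Test (ACT) is in Appendix G.

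Appendix F is a script read to the parent, covering the past 2-4 weeks for symptoms and rescue use. Three stems matter here:

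- Item 1: "how often during the day did _____ have asthma symptoms".
- Item 2: "how often during the night did _____ awake due to asthma symptoms".
- Item 3: "how often during the night did _____ use albuterol, quick relief medicines, for asthma symptoms", followed by the instruction "please do not include albuterol before exercise or heavy play to avoid wheezing due to exercise".

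The severity answers to item 3 are fewer than 2 days a week, ">2d/wk but not daily", daily, and several times a day. The control answers have three levels. The top one is several times a day for ages 5-11, and use throughout the day for ages 12 and over.

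Respondents are told: "Please listen to all the possible responses and then pick the one that best describes the child situation".

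**The concern.** Items 2 and 3 open with the same words, but only item 2 has night-based answers (per month, per week, nightly). Item 3's answers count days of use and uses per day, and the pre-exercise exclusion makes little sense for use at night. The opening looks carried over from item 2. That is an inference, but the mismatch between stem and answers is plain on the page.

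Item 3 is the only Appendix F item on rescue use. A parent who follows the stem leaves daytime use out, while a parent who follows the answers counts it. The form does not record which reading was used, so the same category can mean different things in different children. Section A argues that asthma severity may affect academic performance. A severity measure of uncertain meaning would weaken any description of school outcomes by severity or control.

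**Working it through.** The plan states no figure on this point, so the check compares the text with itself and then works through the item's own answer scale.

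**Stem against answers**

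| Appendix F item | Period named in the stem | Unit of the severity answers |
|---|---|---|
| 1, symptoms | day | days per week, daily, throughout the day |
| 2, waking | night | times per month, per week, nightly |
| 3, albuterol | night | days per week, daily, several times a day |

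Items 1 and 2 agree with their own answers. Item 3 does not.

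**Direction of error.** Let *d* be the days per week with any albuterol use for symptoms and *n* the days per week with such use at night. Night use is part of all use, so *n* ≤ *d*. The answer category never falls as use rises, so category(*n*) ≤ category(*d*). The same holds for uses per day. A literal reading can therefore lower the item 3 category or leave it unchanged, but cannot raise it.

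**Size within the item.** The usage patterns below are assumed for illustration. Exactly 2 days a week is avoided, because the inequality signs may not have survived conversion of the form to text.

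| Assumed use | Severity, all use | Severity, night only | Control, all use | Control, night only |
|---|---|---|---|---|
| 1 day a week, no nights | a | a | a | a |
| 3 days a week, no nights | b | a | b | a |
| 5 days a week, 1 night | b | a | b | a |
| Every day, no nights | c | a | b | a |
| Several times every day, no nights | d | a | c | a |
| Once every night, none by day | c | c | b | b |

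The severity answer drops by 0 to 3 levels and the control answer by 0 to 2.

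**From item to class.** Neither Section D nor Appendix F says how the five items combine into the NAEPP score. Suppose, purely as an assumption, that the worst item sets the class. Item 1 has the same first three severity levels as item 3. A child who needs albuterol every day for daytime symptoms would ordinarily be daily on item 1, so the class would already be at least c whatever item 3 recorded. The class would change only where whole-day rescue use is worse than every other item, for example several uses a day with item 1 at daily (c instead of d). Under another rule the effect would differ.

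**Other sources in the plan**

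- ACT item 4 asks about rescue inhaler or nebulizer use over 4 weeks with no time-of-day limit. It feeds the ACT score, not the NAEPP score. Its form recommends the test from age 12, whereas the study enrols grades 3-8. It has no option between 2-3 times per week and 1-2 times per day, and it does not exclude pre-exercise use.
- The clinician's classification in the Appendix A chart review comes from the IMPACT DC clinic form after a clinic visit. Section D also allows cases from the emergency department.
- Appendix A item 5 records which medicines were used in two days, not how often.

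**The case against.** The strongest reply has four parts.

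1. Parents hear every answer before choosing. Daily and several times a day, together with the exercise exclusion, may prompt them to report all use. This stands in part: it makes understatement possible rather than certain. It also means the item may be read differently by different parents.
2. Rescue use is asked elsewhere. A reader might infer from item 3 that daytime rescue use goes unrecorded in the study. The documents do not support that, because ACT item 4 asks about it and Section D plans the ACT for all cases. The gap is confined to the NAEPP items.
3. A reader might also infer that a child's class is wrong whenever item 3 should have been the worst item, or that severity is understated across the cases. The first needs a scoring rule that the plan does not contain. The second needs to know how parents read the stem and how many cases use albuterol only by day, and neither is given. Item 1 also limits the damage.
4. The consequence is limited. Specific Aim 1 compares GPA with and without asthma, Section E powers the study on GPA above 3.0, and Section E names no analysis by severity. Appendix F is completed by cases only and defines neither group. This stands in full.

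What remains is a fault in a scripted item that feeds a planned score, with a possible error in one direction only.

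**Conclusion.** The point holds as an internal inconsistency in a measurement form. Item 3's stem and answers describe different periods. Read literally, the item can understate rescue use by up to three severity levels or two control levels, and cannot overstate it. These sizes apply to the item under assumed usage patterns, not to the child's class.

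The effect on the overall NAEPP class and the share of cases affected cannot be derived from the documents. Item 1 and ACT item 4 cover the gap in part. The exposure is limited to description or analysis by severity or control among cases. The primary GPA comparison and its power are not touched. The point is still worth correcting, because the remedy costs almost nothing and the ambiguity cannot be resolved from item 3 alone.

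**What to change.** **Where the form is still in use:** remove the words during the night from item 3, so that the stem matches its answers, and keep the answers and the exercise exclusion. This deletes three words. Recruitment was planned for May to November 2016 and the document is dated June 22, 2018, so this step may come too late.

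**For forms completed with the printed wording:** cross-tabulate item 3 against ACT item 4 where both are available, and flag discordant cases. The clearest discordance is the lowest item 3 category alongside an ACT answer of 1-2 times per day or more. Because ACT item 4 counts pre-exercise use and covers a slightly different period, a flag marks a case for caution and does not by itself show misclassification. Report the NAEPP classification with this limitation and with the number flagged.

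**Do not rely on dropping item 3.** Under a worst-item rule, removing an item can only lower the class or leave it unchanged, so it cannot reveal children already classed too low. Under any rule, it cannot recover daytime use that was never recorded.

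The plan should also state how the five items are combined, since the effect of item 3 cannot be judged without that rule. The total cost is one cross-tabulation of data already planned for collection and a few sentences of text, with no new data collection.

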Appendix G

Case# _____

Understanding the Impact of Asthma in Academic Achievement, School Attendance, and in the Quality of Life in Middle school aged children

The American Lung Association recommends everyone 12 years of age and older with asthma take the Asthma Control Test, no matter how well controlled you think your asthma is. Your answers to this 5-question quiz will provide you a score that may help you and your doctor determine if your treatment plan is working or if it might be time for a change.

How to take the Asthma Control Test

Step 1. Write the number of each answer in the score box provided.

Step 2. Add up each score box for your total.

Step 3. Take the test to your doctor to talk about your total score.

1. In the past 4 weeks, how much of the time did your asthma keep you from getting as much done at work, school or at home?

all the time 1	most of the time 2	some of the time 3	a little of the time 4	None of the time 5	
-------------------	-----------------------	-----------------------	---------------------------	-----------------------	----------------------

2. During the past 4 weeks, how often have you had shortness of breath?

More than once a day 1	Once a day 2	3-5 times a week 3	Once or twice a week 4	Not at all 5	
---------------------------	-----------------	-----------------------	---------------------------	-----------------	----------------------

3. During the past 4 weeks, how often did your asthma symptoms (wheezing, coughing, shortness of breath, chest tightness or pain) wake you up at night or earlier than usual in the morning?

4 or more nights a week 1	2-3 nights a week 2	once a week 3	once or twice 4	Not at all 5	
------------------------------	------------------------	------------------	--------------------	-----------------	----------------------

4. During the past 4 weeks, how often have you used your rescue inhaler or nebulizer medication (such as albuterol)?

3 or more times per day 1	1-2 times per day 2	2-3 times per week 3	once a week or less 4	Not at all 5	
------------------------------	------------------------	-------------------------	--------------------------	-----------------	----------------------

5. How would you rate your asthma control during the past 4 weeks?

not controlled at all 1	poorly controlled 2	somewhat controlled 3	well controlled 4	completely controlled 5	
----------------------------	------------------------	--------------------------	----------------------	----------------------------	----------------------

